The Friendship Bench is an ideal psychotherapy intervention to integrate with PrEP delivery in South Africa for a variety of reasons. First, it was designed for and tested in a similar African setting and would therefore need less adaptation for public clinics in South Africa than an intervention developed in a very different context. Second, it was recently adapted to improve medication adherence among PLWH in Southern and Eastern Africa and to improve symptoms of common mental disorders for adolescents and young adults. While these adaptation studies are underway, initial data suggests that the intervention is feasible and acceptable for delivery with HIV medication and among young people.74,104-¹⁰⁷ Third, our prior quantitative and qualitative work confirms that common mental disorders are prevalent among AGYW attending PrEP services and this population would likely benefit from a PST approach that could help them address and cope with underlying causes of poor mental health (HIV and PrEP stigma, GBV, food and financial insecurity, relationship power dynamics; Figure 3), A PST intervention would also have likely benefits beyond improved mental health and PrEP adherence, by empowering young women in their lives and relationships and reducing risk of HIV and negative sexual and reproductive health outcomes more broadly. Fourth, our prior PrEP studies (PrEP SMART, HPTN 082, EMPOWER), demonstrated that young women in Johannesburg are willing to open up to young female counselors and discuss mental health challenges with them and they find this type of problemfocused counseling appealing and acceptable when delivered alongside PrEP services. The Friendship Bench approach also has the potential to be scalable in the South African PrEP delivery context because it is meant to be delivered by lay counselors (rather than already over-burdened clinic staff), can be administered in only 4-6 sessions, and, if effective, would provide a useful referral option for young women who screen positive for symptoms of common mental disorders at their PrEP visits according to South African standard-of-care guidelines for adults in primary and HIV care.¹⁰⁸ This approach would also be consistent with WHO guidelines on integrating PrEP within a package of adolescent-friendly and differentiated health services that tailor support to those at greatest need. 6,33

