Youth Friendship Bench SA + Standard-of-Care: The Youth Friendship Bench SA intervention includes: five individual counseling sessions conducted at Enrollment, Week 2, Week 4, Week 8, and Week 12; one optional in-person or WhatsApp-based group counseling session between Week 8 and Week 12; optional remote counseling sessions; and optional one-way SMS messages to provide reminders about upcoming visits. Individual counseling sessions will last up to 60 minutes. Participants will meet with a lay counselor to complete common mental disorder screening via an intervieweradministered SRQ-20 form (Appendix 2) during their visits at screening/enrollment, Week 4, and Week 12. During the initial Youth Friendship Bench SA session, participants will meet with the trained counselor to discuss mental health challenges, identify problems in their life that affect their mental health and PrEP use, generate alternative solutions, make decisions about the alternatives, and collaboratively decide on a plan to implement the solutions. The counselor will review the participant's SRQ-20 form prior to session start to identify salient mental health concerns and symptoms and will use that to guide the initial discussion with the participant. During follow-up counseling sessions, participants will discuss progress in implementing solutions to address the problems they identified in prior sessions with the lay counselor. They will also discuss any other mental health challenges and problems in their life that affect their mental health and PrEP use which they would like to address. During the Week 4 and 12 visits, counselors will also reference the completed SRQ-20 tool for key areas to probe around symptoms of common mental disorders and any symptom changes since the last visit. Group counseling sessions will last up to 120 minutes. Participants in the Youth Friendship Bench SA arm will be offered the choice of completing remote counseling sessions at Weeks 2 and 8 and receiving oneway SMS appointment reminder messages to plan for upcoming clinic visits. See Section 4.2 below for additional information on lay counselor training and supervision.

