8.2. Lay Counselor Training and Supervision

Training: All Youth Friendship Bench SA counseling sessions will be conducted by one of two lay counselors, young women between approximately 24-30 years of age. These lay counselors will be trained by the protocol team during a one-week intensive training and will receive weekly in-person supervision by the study's research psychologist (**Appendix 3**). The training materials were developed and tested by the Friendship Bench team in Zimbabwe and have been used in a number of Friendship Bench adaptations globally.^{95,96,105} They include didactic sessions on common mental health conditions, symptom identification including screening tools like the SRQ-20, person-centered counseling skills, active listening, and problem-solving therapy techniques. The training is also designed to include time for practicing counseling skills throughout the week and to provide space for counselors to process their own feelings and stressors during the training. We will adapt the training materials as needed to ensure they are appropriate for young lay counselors in our population.

Supervision: Counselors will keep a progress note for the session. Sessions may be audiorecorded to ensure fidelity to the counseling messages and these audio-recordings will be reviewed with study team members in the US for remote supervision meetings with the counselors and the study team on a monthly basis. Participants will be asked whether they consent to having their counseling sessions audio-recorded as part of the enrollment consent process and will be informed that they can withdraw their consent for recording at any time. The study research psychologist will also conduct in-person supervision meetings with the counselors on a weekly basis, to discuss counseling progress, troubleshoot any difficult cases, and process any feelings of their own that are brought up during the counseling sessions.

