8.3.4. Week 4 Visit

- 1. Confirm consent
- 2. Confirm locator information and update as needed
- 3. Collect psychosocial and behavioral data additional data (see Section 6).
- 4. Assess symptoms of common mental disorders
 - a. All participants will receive assessments per APC guidelines and referrals as needed. They will also complete the SRQ-20 with the lay counselor.
 - b. Participants Youth Friendship Bench SA arm will complete their 3rd counseling session.
- 5. Schedule participant's next visit
 - a. Standard-of-care participants will be scheduled for their Week 12 visit in 60 days.
 - b. Youth Friendship Bench SA participants will be scheduled for their Week 8 visit in 30 days. They will be offered the option to complete the Week 8 visit in-person or remotely (over the phone).
- 6. All participants will be asked to provide a urine sample for the tenofovir (TFV) point-of-care (POC) assay. Urine POC assay testing and drug-level feedback counseling based on assay results will be conducted by the lay Youth Friendship Bench SA for participants in both arms and proceed as described in Section 5.1.2. The urine assay results will be used for research purposes only and will not be included in the clinic record.
- 7. Schedule in-depth interviews for AGYW between the Week 4 and Week 12 study visit.

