8.3.6. Week 12/Exit Visit

- 1. Collect psychosocial and behavioral data (see Section 6)
- 2. Assess symptoms of common mental disorders
 - a. All participants will receive assessments per APC guidelines and referrals as needed. They will also complete the SRQ-20 with the lay counselor.
 - b. Participants Youth Friendship Bench SA arm will complete their 5th counseling session.
- 3. All participants will be asked to provide a urine sample for the tenofovir (TFV) point-of-care (POC) assay. Urine POC assay testing and drug-level feedback counseling based on assay results will proceed as described in Section 5.1.2. The urine assay results will be used for research purposes only and will not be included in the clinic record.
- Complete termination procedures: exit participants, record any serious adverse events, ensure that participant is linked to and returns to the clinic for any routine services, and remove participants from any SMS communication as needed.

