10.0 DATA COLLECTION

10.1. Quantitative data collection

Demographic and behavioral data will be collected, including information on symptoms of common mental disorders, drug and alcohol use, GBV, post-traumatic stress symptoms, coping behavior, self-esteem, sexual relationship power, and sexual behavior (e.g., number of partners, vaginal sex with partners).

We will access the participant's clinic record to obtain information on age, HIV status, and PrEP status at screening. We will also abstract information on PrEP refills (bottle dispensed, dates of dispensation, and PrEP terminations) from the clinic records during the participant's three-month follow-up period.

Symptoms of common mental disorders will be assessed using the SRQ-20, which will be interviewer-administered by the lay counselors at enrollment, Week 4, and Week 12. Data on depressive symptoms (using the Patient Health Questionnaire-9 [PHQ-9]), anxiety (the Generalized Anxiety Disorder questionnaire [GAD-7]), history of mental health conditions and

services received, drug and alcohol use, GBV, and post-traumatic stress symptoms will also be interviewer-administered on study Case Report Forms (CRFs). All other demographic and behavioral data will be self-collected by participants using a tablet application. Research staff will be available in the clinic to provide guidance and assistance in completing the questionnaire as needed. De-identified data will be collected using REDCap and stored on a secure server.

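### Missed-visit follow-up is listed for one arm only and no analysis departs from missing at random; separately, the SRQ-20 is asked by the unmasked counselor role that delivers the intervention

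*Protocol*

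**What the plan says.** **Follow-up.** Protocol 8.4 lists retention procedures that may be used. Active follow-up of missed visits and SMS reminders are each restricted to the intervention arm; locator updating, mapping of residences and urine feedback are not. Section 8.3.2 says SOC women get neither reminders nor remote services. Section 8.3.8 promises an effort to obtain final evaluations from women who leave early, without limiting it to one arm. Section 12.1.6 compensates participants at enrollment, Week 4 and Week 12, again without restriction by arm. Section 9.1.2 offers only a hypothesis that urine feedback will help keep SOC women.

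**Missing data.** The Missing data paragraphs under SAP Co-Primary Analyses 1 and 2 plan 100 imputations under MAR. Complete-case analysis is allowed in stated circumstances, a 10% threshold governs imputing outcomes, and results are labelled hypothesis-generating above 40% missing. The SAP will look at what predicts missingness but names no auxiliary variable. Its only analysis labelled sensitivity adjusts adherence for baseline imbalance.

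**SRQ-20 interviewer.** Section 10.1 describes the SRQ-20 as an instrument "which will be interviewer-administered by the lay counselors at enrollment, Week 4, and Week 12". Section 8.3.4 says of all participants: "They will also complete the SRQ-20 with the lay counselor"; section 8.3.6 repeats this for Week 12. Section 8.2 says "All Youth Friendship Bench SA counseling sessions will be conducted by one of two lay counselors". At the Week 12 visit, "Participants Youth Friendship Bench SA arm will complete their 5th counseling session", and under section 7.1 "counselors will also reference the completed SRQ-20 tool for key areas to probe around symptoms of common mental disorders". The masking text in section 11.1 speaks of investigators, not counselors or interviewers.

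**The concern.** Two separate routes to bias are left open.

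First, both co-primaries are measured at Week 12. If women in one arm are pursued after a missed visit and women in the other are not, loss may differ by arm. If the missing also differ in outcome, MAR imputation corrects this only as far as its predictors explain the loss. Those predictors are not named, and nothing planned shows how far the RR depends on the assumption.

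Second, the SRQ-20 is self-reported, is cut at 7 and is asked by the role that delivers the counseling. Neither document says whether a counselor may interview her own client. Disclosure could then differ by arm, in a direction the protocol does not settle. Section 5.1 reports that "young women in Johannesburg are willing to open up to young female counselors", while section 5.2 reports reluctance to open up and fear of judgment. More disclosure by counseled women would hide benefit; a wish to please the counselor would inflate it.

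**Working it through.** **Plan's own figures.** 110 women, 1:1, so 55 per arm. Retention of 85-90% (11.3) means 11 to 16.5 missing of 110. For the SRQ-20 the plan claims 80% power for 50% vs 75%. The two-sided normal approximation with all 55 per arm gives Φ[(0.25 − 1.96·√(2·0.625·0.375/55)) / √((0.25 + 0.1875)/55)] = Φ(0.0691/0.0892) = 78.1%. This is close to the claim, but at 90% and 85% retention it falls to 73.6% and 71.1%. The point below does not depend on this power.

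**1. Unequal loss.** The split by arm is assumed; both splits average 12.5% missing, above the SAP's 10% threshold. Let t be the true rate, m the fraction missing and a the rate among the missing.

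- Observed rate o = (t − m·a)/(1 − m).
- Rate imputed for the missing = o + k·(a − o), where k = 0 means uninformative predictors and k = 1 fully informative.
- Arm estimate = (1 − m)·o + m·(imputed rate); the RR is the ratio of arm estimates.

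Example with k = 0: intervention (0.60 − 0.10·0.10)/0.90 = 0.656; SOC (0.40 − 0.15·0.10)/0.85 = 0.453; RR 1.45.

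| True rates, intervention vs SOC | a | Loss | k=0 | k=0.5 | k=1 |
|---|---|---|---|---|---|
| Adherence 60% vs 40% | 10% | 10% vs 15% | 1.45 | 1.47 | 1.50 |
| | 10% | 5% vs 20% | 1.32 | 1.40 | 1.50 |
| | 30% | 10% vs 15% | 1.52 | 1.51 | 1.50 |
| | 30% | 5% vs 20% | 1.45 | 1.47 | 1.50 |
| Adherence 40% vs 40% | 10% | 10% vs 15% | 0.96 | 0.98 | 1.00 |
| | 10% | 5% vs 20% | 0.88 | 0.93 | 1.00 |
| SRQ-20 <7, 75% vs 50% | 25% | 10% vs 15% | 1.48 | 1.49 | 1.50 |
| | 25% | 5% vs 20% | 1.38 | 1.44 | 1.50 |

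The sign is not fixed. With no true SRQ-20 effect (50% each), 10% vs 15% loss, and missing rates of 25% (intervention) and 75% (SOC), the observed rates are 0.475/0.90 = 0.528 and 0.3875/0.85 = 0.456. The RR is then 1.16.

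**2. Tipping example, SRQ-20 (counts assumed).** Retain 50 and 47, with 38/50 vs 24/47 below 7. Then log RR = 0.398 and SE = √(0.240/38 + 0.489/24) = 0.163, so RR = 1.49 (95% CI 1.08-2.05), p = 0.015. Now fill in the missing, with none of the 5 intervention women below 7. If 3 of the 8 SOC women are below 7, p = 0.038; if 4 of 8, 38/55 vs 28/55 gives p = 0.057. This fills in fixed values and ignores imputation variance.

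**3. Reporting shift, SRQ-20 (sizes assumed).** Exact enumeration of two binomials for every n from 47 to 55 per arm; two-sided Wald test on log RR with variance Σ(1 − p)/(np), which is the robust Poisson variance when arm is the only predictor.

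- True 50% in both arms: rejection 3.9-5.4% with no shift; 4.5-6.2%, 6.6-8.4% and 15.4-17.6% when the intervention arm is recorded 2.5, 5 and 10 points too high.
- True 75% vs 50%: power 70-77%, falling to 50-56% if the intervention arm is recorded 5 points too low.

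**The case against.** **This is a hybrid trial, so unequal contact may be part of what is tested.** SMS reminders plainly are: section 7.1 puts them in the package, and they can stay. Tracing missed visits is not in that description. The fuller list of adaptations in section 5.2 is not legible in the text available, so whether tracing belongs to the package cannot be settled. Either way, outcome visits can be traced equally without giving SOC women any counseling.

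**The asymmetry is smaller than 8.4 alone suggests.** This stands. Compensation at the outcome visits, locator updates, mapping, the early-exit commitment and DSMB review of retention (9.5) cover both arms, and SOC visits follow the refill schedule (7.1). A reader might infer that SOC women are not pursued at all, but section 8.3.8 contradicts that.

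**The missing-data bias may be small.** This also stands. At 10% vs 15% loss the RR moves by at most 0.05, against a 95% CI of about 0.99-2.28 (SE = √(0.4/(0.6·49.5) + 0.6/(0.4·46.75)) = 0.213). The larger shifts need a fourfold difference in loss and weak predictors, and the SAP expects to find informative variables. A reader might infer that greater SOC loss must pull both RRs toward or below 1; the 1.52 and 1.16 results show otherwise.

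**The interviewer concern has partial answers.** The Week 12 schedule lists the SRQ-20 before the fifth session, and at Week 4 the counselors also do urine testing and feedback in both arms. The SAP analyzes PHQ-9, GAD-7 and PCL-5 separately, so discordance with the SRQ-20 would be visible. These scales are self-reported too and their interviewers are unnamed, so they are a partial check and not a correction. The claim that nothing planned could reveal a problem would be too strong. So would a claim that the SRQ-20 result is biased: nothing in the documents supports a shift of any given size or sign.

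**Conclusion.** The point holds in limited form. Follow-up of missed outcome visits is partly unequal as written, and sections 8.3.8 and 8.4 need reconciling. Both co-primaries rest on MAR with unnamed auxiliaries and no test of that assumption, although 10-15% loss is expected. The resulting bias ranges from nil (fully informative predictors) to a true adherence RR of 1.50 read as 1.32 (5% vs 20% loss, 10% of the missing adherent, uninformative predictors). All splits by arm and outcomes among the missing are assumptions; the documents give neither.

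Separately, the SRQ-20 interviewer is unmasked and may be the participant's own counselor. The effect is of unknown size and direction: immaterial at a 2.5-point shift, material at 10 points.

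**What to change.** **(a) Follow-up.** Trace missed Week 4 and Week 12 outcome visits in the same way in both arms, and keep SMS reminders as an intervention component. Reconcile 8.3.8 with 8.4. Show retention by arm at the DSMB review already planned after 50% enrollment (9.5). Cost: contacting about 6-8 of 55 SOC women (55 × 10-15%), or 11 at an assumed 20%. The downside is slightly more SOC contact than routine care.

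**(b) SAP, both co-primaries.** Add a delta or tipping-point analysis with delta varied separately by arm. Name the refill and termination records as imputation auxiliaries; they are already collected, since section 10.1 says "We will also abstract information on PrEP refills". Counting the missing as non-adherent should be one scenario only, because alone it favors the better-traced arm. With true 40% in both arms and 40% of the missing adherent, it gives 0.36/0.34 = 1.06 at 10% vs 15% loss and 0.38/0.32 = 1.19 at 5% vs 20%. Cost: SAP text and analysis time.

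**(c) Interviewer.** Where scheduling allows, have the counselor who did not treat the participant administer the Week 4 and Week 12 SRQ-20, and pass the form on so that its use in the session is unchanged. State in 11.1 that counselors and SRQ-20 interviewers are not masked. Cost: some scheduling and one sentence. This removes own-client interviewing but does not mask the interviewer.

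Moving the SRQ-20 to tablet is not proposed, although section 10.1 says "All other demographic and behavioral data will be self-collected by participants using a tablet application". Section 12.1.3 provides for women who are not literate, section 9.1 ties follow-up questions to the suicidal-ideation item, and a change during enrollment would split the mode of administration.

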10.2. Qualitative data collection

The use of qualitative methods that give young women, staff, and key informants the opportunity to discuss their opinions on the acceptability, appropriateness, and feasibility of Youth Friendship Bench SA in their own words will result in a more culturally-sensitive and potentially scalable approach to integrated mental health and PrEP adherence support among young women in Africa. Interviews will be conducted with a purposive sample of up to 30 young women and 15 clinic staff and key informants (with sampling until we reach saturation of themes), and will include:

- 1. Young women in both the Youth Friendship Bench SA and standard-of-care arms, with varying levels of PrEP adherence (based on Week 4 urine POC assay results) and common mental disorder symptom severity (based on Enrollment and Week 4 SRQ-20 scores)
- Clinic staff involved in the delivery of the Youth Friendship Bench SA and standard-of-care mental health and PrEP services including the lay counselors providing the Youth Friendship Bench SA intervention.
- Key informants involved in mental health and/or PrEP service provision, programs, funding, and/or policy-making.

In-depth gualitative interviews will occur sometime between the Week 4 and Week 12 study visits (for young women) and throughout the study period (for staff and key informants). The interviews with young women will explore the decision to take PrEP, barriers and facilitators to PrEP adherence, experiences with symptoms of common mental disorders and any links between these symptoms, HIV risk, and PrEP use, perceptions of standard-of-care service delivery, perceptions of Youth Friendship Bench SA service delivery (including satisfaction with the intervention, perceived benefits, challenges with the intervention, recommended changes, and perceived acceptability, appropriateness, and feasibility for delivery in PrEP clinics), and suggestions for future integrated mental health and PrEP adherence interventions. Interviews with clinic staff and key informants will focus on perceptions of standard-of-care service delivery, perceptions of Youth Friendship Bench SA service delivery (including satisfaction with the intervention, perceived benefits, challenges with the intervention, recommended changes, and perceived acceptability, appropriateness, and feasibility for delivery in PrEP clinics), and suggestions for future integrated mental health and PrEP adherence interventions. All interviews will be up to 60 minutes. We will also ask participants in both arms about the acceptability of the urine POC assay for PrEP adherence assessment and their receipt of counseling based on their urine assay results. All qualitative participants will be asked to provide written informed consent to participation and to having their interviews audio-recorded so that data can be used for subsequent analysis and publication. All interviews discussions will be conducted in the participant's preferred language.

Interview guides will be developed using reviews of local literature and youth community advisory board (YCAB) feedback. The semi-structured qualitative interview guide will provide a general structure for discussion but will allow interviewers and respondents to explore unique themes for a given interview. Local researchers/ethnographers will conduct all qualitative interviews with oversight from the protocol team and approximately one social scientist. All interviews will be audio-recorded and transcribed and translated into English by trained site staff.

When conducting a qualitative exploration, the sampling method should be designed to include a range of possible perspectives on the phenomenon under study, thus ideal qualitative samples are purposive in nature. The proposed study will utilize a stratified purposive sample, which will allow for consideration of the concepts of range, saturation/redundancy, and stratification in the sampling frame. We also took into account feasibility when creating our sample sizes, a factor that is especially relevant in qualitative research with "hard-to-reach" populations such as youth. We will stratify the sample based on PrEP adherence, intervention arm, and symptoms of common mental disorder as described above. Stratification on these factors will allow for a diverse purposive sample that will include a range of types of young women who may have various experiences with mental health issues, PrEP adherence, and the Youth Friendship Bench SA intervention. We will also conduct debriefs with the qualitative interviewers and the counseling staff to explore their views on participant's experiences with the in-depth interviews and the interventions.

All qualitative interview recordings and transcripts will be de-identified and will be stored on a secure server for at least two years at the University of the Witwatersrand. De-identified transcripts will be provided to the University of California San Francisco where they will be stored for three years after completion of the study.

In addition to data collection using in-depth interviews, we will also conduct ethnographic nonparticipant observations of clinic activities. A trained social scientist interviewer will observe participant waiting room discussions and comfort in the clinic, clinic flow, and the clinic environment for AGYW. Non-participant observations will allow the research team to observe interactions and clinic activities as a "fly on the wall" but otherwise remain as an identified outsider.^{121,122} One weakness of overt non-participant observation is the potential that participants may change their behavior because they are aware of being observed. However, this effect on participants' behavior has been shown to wane over time, even as observations continue.¹²³ We will conduct up to 2 clinic observations per month during the duration of the study and the social scientist will complete field notes describing key learnings from the observation (without any specific identifiers). Prior to beginning an observation session, the social scientist will announce himself or herself in the waiting room. Observation data will be considered process notes to inform study activities, rather than research data to advance generalizable knowledge. Data will be stored on a secure server and reviewed periodically through the study.

